### 8.6. Pre-Discharge and Follow-up Assessments

The subject will be required to complete follow up visits through 12 months post index ablation procedure. Discharged subjects will receive a telephone call at 7 days post ablation procedure to assess any occurrence of Adverse Events; otherwise, any Adverse Events can be found in subjects' in-hospital source records. Additional follow-up visits are to be conducted at 1 month, 3 months, 6 months, and 12 months post index procedure. Follow-up visits and/or calls should be scheduled according to the following timeframes: 7 day (7D, day 7-14), 1 month  $\pm$  7 days (1M, day 23-37), 3 month  $\pm$  14 days (3M, day 76-104), 6 months  $\pm$  30 days (6M, day 150-210), and 12 month  $\pm$  45 days (12M, day 315-405). Follow-up visit schedule will not reset if subject undergoes a repeat AF ablation procedure.

Pre-Discharge / Follow-up assessments and data to be collected are described below.

- **Cardiac Medication Regimen:** All cardiac medication prescribed since the ablation procedure until the end of follow-up will be recorded, including the type and name of the medication, associated indications, start and end dates, etc. Data will be collected at the pre-discharge visit, the 7 day, 1M, 3M, 6M, and 12M follow-up, and at any unscheduled visits.
- **Anticoagulation Medication Regimen:** Information is to be collected at the pre-discharge visit, 1M, 3M, 6M, and 12M follow-up, and at any unscheduled visits.
- **Physical Exam (including standardized neurological assessment and cardiovascular/ pulmonary examination):** Physical Exam is to be performed by a physician at discharge and physician, physician assistant, or nurse practitioner at subsequent clinical visits (1M, 3M, 6M (if clinical visit), and 12M visits). The following items will be evaluated as part of the standardized neurological assessment: vision, hearing, speech, level of consciousness, orientation and ability to move all extremities. If the neurological assessment demonstrates abnormal findings, the subject should have a formal neurological consult and examination with appropriate imaging (i.e., DW-MRI), used to confirm any suspected diagnosis of stroke.

- **Quality of Life questionnaire: AFEQT™** is to be collected at the 3M, 6M (if clinical visit), and 12M visits.
- **Transthoracic Echo (TTE):** TTE should be conducted within 48 hours of the index procedure. Equivalent exams may be substituted if needed and clinically acceptable.
- **Electrocardiogram (12-Lead ECG):** Data from 12-lead ECG recordings will be collected at the 3M and 12M follow-up visit. ECG data will be collected at baseline, pre-discharge, 1M follow-up visit, and unscheduled visits if completed as standard of care and at 6M if a clinical visit occurs and ECG is completed as standard of care. If an ECG is unable to be obtained (e.g. due to telemedicine visit), subjects will be instructed to transmit 1 TTM transmission (60 seconds) in lieu of an ECG recording at the time of the follow-up visit. Any 12-lead ECG tracings obtained beyond 3 months (90 days) showing an arrhythmia will be reviewed and adjudicated by an independent cardiologist.
- **Transtelephonic Monitoring (TTM):** Subjects will be provided with a TTM device no later than at the 1M follow-up visit (TTM device may be provided at discharge if collected as standard of care) and required to record and transmit a minimum of 1 transmission (60 seconds) every week through the end of month 5 of follow-up. Starting at month 6 of follow-up, subjects will be required to record and transmit a minimum of 1 transmission (60 seconds) every month until the effectiveness evaluation period is completed (12 months post index procedure). Subjects will also be instructed to transmit any symptom-triggered episode that occurs from the time they receive the TTM device through the 12M follow-up visit. A core lab will be used to evaluate and assess the TTM tracings.
- **24 Hour Holter:** Holter monitor will be used at the 12M follow-up visit to monitor the subjects' heart rhythm for 24 hours continuously. A core lab will be utilized to evaluate and assess the 24-hour Holter recordings.
- **Cardiac Multi Slice CT/MRA Image:** CT/MRA will be completed at the 3M follow-up visit for subjects in the CT/MRA subset. In addition, any subjects who have symptoms suggestive of PV stenosis should undergo CT/MRA imaging. Post procedure CT/MRA should be performed with contrast, unless there is a contraindication, and must be of sufficient quality to evaluate the number, size and anatomy of the pulmonary veins. All CT/MRA images collected for the study should be sent to the study core lab.
- **Adverse Events:** AEs must be collected from the time the subject signs the informed consent onwards.
- **AFL/AT/AF recurrence:** Any post-procedure atrial arrhythmia that is documented by devices other than the sponsor provided TTM/Holter Monitor and/or ECG will be recorded at 1M, 3M, 6M, and 12M follow-up as well as at any unscheduled visits.
- **Repeat Ablation:** Any ablation procedure performed after the index procedure will be recorded at 1M, 3M, 6M, and 12M follow-up as well as at any unscheduled visits.

For NAE subjects:

- **Cerebral MRI** is required to be performed between 12-48 hours (preferably between 24-48 hours) post index procedure to evaluate the presence/absence of cerebral lesions and/or neurological defects. If there are findings noted on the post-ablation cerebral MRI, a follow-up MRI will be required at each follow-up visit until resolution is observed. Cerebral MRIs will be analyzed by a central core lab to

determine the number, size, and anatomical location of cerebral micro-emboli, if any. See appendix A for methodology.

- **Neurological Exam** is required to be performed between 24-48 hours post index procedure to evaluate the neurological condition and presence of neurological deficits occurring post study ablation procedure. The Neurological Exam may be performed earlier than 24 hours if neurological symptoms/signs developed post ablation. If there are findings of microemboli/neurologic deficits, a follow-up neurologic exam will be required at each follow-up visit until resolution is observed. A certified/qualified neurologist, blinded to the MRI data, must perform neurologic exams.
- **National Institutes of Health Stroke Scale (NIHSS)** assessment is required to be performed between 24-48 hours post index procedure to evaluate the neurological condition and presence of neurological deficits of the subject's post study ablation procedure. The NIHSS can be administered earlier than 24 hours if neurological symptoms/signs developed post ablation. If there are findings of microemboli/neurologic deficits, a follow-up NIHSS assessments will be required at each follow-up visit until resolution is observed. This assessment will be performed by site staff certified in the administration of the NIHSS
- **Modified Rankin Scale (mRS)** assessment is required to be performed at the 1 month follow-up visit to evaluate the neurological condition and presence of neurological deficits occurring post study ablation procedure. If there are findings of microemboli/neurologic deficits, follow-up mRS assessments will be required at each follow-up visit until resolution is observed. This assessment will be performed by site staff certified in the administration of the mRS.
- **Mini-Mental State Examination (MMSE)** is required to be performed at the 1 month follow-up visit to assess changes in cognitive status post study ablation procedure. If there are findings of microemboli and/or new cognitive deficits, follow-up MMSE assessments will be required at each follow-up visit until resolution is observed. The MMSE will be performed by site staff with documented training in the administration of such tools.

### 8.7. **Unscheduled visit**

If a subject returns for a potential study related cardiovascular or neurological visit outside of the protocol-defined visit schedule provided in Table 8.9A, the visit will be considered "unscheduled" (UNS). An Investigator may request an unscheduled visit in the presence of a new or worsening cardiovascular condition or neurological deficit. If the unscheduled visit is for a repeat ablation procedure, the protocol follow-up schedule is based on the index ablation procedure. For all unscheduled visits, an unscheduled visit eCRF must be completed and the subject must also return for their next scheduled study visit.

### 8.8. **Schedule of Events Table**

At each visit, the following assessments should be performed (Equivalent exams may be substituted if needed).

**Table 8.8A: Summary of Subject Assessments**

Assessments	Pre- Procedure	Pre- Discharge Post procedure - Discharge	D7  D7- 14	M1 D23- 37	M3 D76- 104	M6  D150- 210	M12 D315- 405	UNS
Patient Informed Consent/ Demographics	● 							
Height and Weight	● 							
Physical exam	● 	●		●	●	● 	●	●
Medical/AF history	● 							
Cardiac Medication Regimen 	● 	●	●	●	●	●	●	●
Anti-coagulation Regimen 	● 	●		●	●	●	●	●
CHA 2 DS 2 -Vasc Score	● 							
NYHA functional Class Scale	● 							
Pregnancy Test	● 							
QoL (AFEQT™ questionnaire) 	● 				●	● 	●	
TTE	● 	● 						
LA thrombus detection (TEE/ICE)	● 							
ECG	● 	● 		● 	●	● 	●	● 
TTM 				●	●	●	●	●
24-hour Holter 							●	
Cardiac CT/MRA	● 				● 			● 15a
Adverse events 	●	●	●	●	●	●	●	●
AFL/AT/AF recurrence 				●	●	●	●	●
Repeat Ablation				●	●	●	●	●
Cerebral MRI (NAE subjects only)	● 	● 		● 	● 	● 	● 	● 
Neurological Exam (NAE subjects only)	● 	● 		● 	● 	● 	● 	● 
NIH Stroke Scale (NAE subjects only)	● 	● 		● 	● 	● 	● 	● 
mRSE (NAE subjects only)	● 			●	● 	● 	● 	● 
MMSE (NAE subjects only)	● 			●	● 	● 	● 	● 

1. May be telephone call, virtual visit, or clinic visit.
2. Completed/Collected within 90 days prior to ablation procedure.
3. Required only for clinical visit
4. May be completed via telephone call or virtual visit when a clinic visit is not possible.
5. Completed/Collected in subjects with congestive heart failure.
6. In all women of childbearing age and potential. To be completed within 72-hours prior to ablation procedure.
7. To be completed within 48 hours post-index procedure.
8. To be completed the day before or the day of the study ablation procedure.
9. To be collected if completed as standard of care.
10. To be completed if a clinical visit occurs and if collected as standard of care
11. Refer to section 8.6, Pre-Discharge and Follow-up Assessments, for TTM transmission requirements
12. Completed/Collected within 6 months prior to ablation procedure
13. Required for subjects in the CT/MRA subset
14. If AE results in Hospitalization, associated cost data should be collected
15. Some adverse events may require specific tests/assessments to be conducted
  - a. Subjects with symptoms suggestive of PV stenosis should undergo CT/MRA imaging
  - b. Subjects with symptoms suggestive of thromboembolism, phrenic nerve paralysis, and/or stroke/CVA should undergo the assessments described in the corresponding sections of Table 9.2.3A
  - c. Subjects whose post-procedural fluoroscopic evaluation of the diaphragm demonstrates diaphragmatic paralysis should undergo appropriate follow-up test (e.g. sniff test or inspiration/expiration chest radiography) at discharge and subsequent follow-up visits until resolution of the diaphragmatic paralysis or the completion of the study (diaphragmatic paralysis is considered to be permanent when it is documented to be present 12 months).
16. To be completed within 72-hours prior to ablation procedure.
17. To be completed between 12-48-hours post-procedure.
18. To be undertaken if neurologic symptoms and/or cerebral ischemic lesions identified in a prior evaluation (if undertaken, then clinical visit is needed).
19. To be completed only if a previous mandated test was missed, or if subject reports neurologic difficulties between scheduled follow-up visits and unscheduled assessment per investigator approval.
20. To be completed between 24-48-hours post-procedure.

## 9. Assessment of Safety

### 9.1. Specific Safety Parameters

‡ Pursuant MDR 2017/745, in the occasion relevant (local) regulations, guidance(s) and processes on safety determinations, definitions and reporting become in full force during the course of the study, the Sponsor shall adhere to the applicable definitions and processes.

### 9.2. Adverse Event Definitions

#### 9.2.1. Adverse Events (AE)

An AE is any untoward medical occurrence in a subject whether or not related to the investigational medical device. Specifically, an adverse event (AE) is any undesirable experience (sign, symptom, illness, abnormal laboratory value, or other medical event) occurring to a subject during the course of the study, whether or not it is related to the device or procedure.

The following clinical events **will not be considered an adverse event for this clinical study:**

- Any medical condition that is present at the time of screening. Such conditions should be added to the medical history, if not previously reported. However, if the study subject's condition deteriorates at any time during the study, it should be recorded as an AE.
- A trace / trivial / minor pericardial effusion that is asymptomatic, requires no medical intervention, and does not extend hospitalization will not be considered an adverse event
- Minor pericarditis attributable to the ablation procedure defined as pleuritic chest discomfort with or without pericardial rub and ECG changes.
- Recurrence of pre-existing AF/AT/AFL
- AF/AFL/AT recurrence requiring DC cardioversion during the blanking period and/or pharmacological cardioversion at any time throughout the duration of the study. However, new onset of left atrial flutter occurring post-ablation is an AE.
- Re-ablation for AF or pre-existing AFL/AT itself is not an AE, however any complication associated with the repeat ablation procedures is considered an AE and shall be reported within the applicable timelines.

#### 9.2.2. Serious Adverse Event (SAE)

A serious adverse event (SAE) is any event that meets one or more of the following criteria:

- Leads to a death
- Leads to a serious deterioration in the health of a subject that resulted in:
  - A life-threatening illness or injury
  - A permanent impairment of a body structure or a body function
  - In-patient hospitalization or prolongation of an existing hospitalization\*
  - Medical or surgical intervention to prevent life-threatening illness or injury or permanent impairment to body structure or a body function
  - Chronic disease (MDR 2017/745) ‡
- Leads to fetal distress, fetal death or a congenital abnormality or birth defect.

\*Planned hospitalization for a condition present prior to the subject's enrollment in the study will not meet the definition of an SAE. An AE would meet the criterion of "hospitalization" for seriousness if the event necessitated an admission to a health care facility (e.g., an overnight stay). Emergency

room visits that do not result in admission to the hospital should be evaluated for one of the other serious outcomes.

### 9.2.3. Primary Adverse Event

A Primary AE is an event listed in Table 9.2.3A which occurs within the first week (7 days) of an ablation procedure which used one or more of the investigational device(s) unless otherwise indicated.

**Table 9.2.3A: Primary Adverse Events**

Primary Adverse Event	Description / Criteria
Death*	Subject death directly related to the device or procedure that occurs at any time during or after the procedure.
Atrio-Esophageal Fistula*	Defined as a connection between the atrium and the lumen of the esophagus. Evidence supporting this diagnosis includes documentation of esophagus erosion combined with evidence of a fistulous connection to the atrium such as air emboli, an embolic event, or direct observation at the time of surgical repair. A CT scan or MRI scan is the most common method of documentation of an atrio-esophageal fistula.
Myocardial Infarction	
Presence of any one of the following criteria:
 
 
• Detection of ECG changes indicative of new ischemia (new ST-T changes or new left bundle branch block [LBBB]) which persist for more than 1 hour
 
• Development of new pathological Q waves on ECG
 
• Imaging evidence of new loss of viable myocardium or new regional wall motion abnormality
 

Cardiac Tamponade**/ Perforation	
The development of a significant pericardial effusion during or within 30 days of undergoing the index AF ablation procedure. A significant pericardial effusion is one which results in hemodynamic compromise, requires elective or urgent pericardiocentesis, or results in a 1 cm or more pericardial effusion as documented by echocardiography.
 
 
• Cardiac tamponade/perforation should also be classified as: 
 
○ Early – diagnosed prior to discharge
 
○ Late – following initial discharge from the hospital
 
 
 

Thromboembolism	
Formation of a clot (thrombus) inside a blood vessel causing obstruction to blood flow accompanied by clinical symptoms. The thrombus can migrate (embolus) and obstruct distal vascular sites. Diagnostic tests to help detect thromboembolisms may include but are not limited to angiography (pulmonary or distal), ventilation-perfusion (V/Q) scans, venography, Doppler ultrasonography, spiral CT, and echocardiography.
 
For the purposes of this study silent (asymptomatic) cerebral embolism will not be considered a PAE.

Primary Adverse Event	Description / Criteria
Transient Ischemic Attack	New focal neurological deficit with rapid symptom resolution (usually 1 to 2 hours), always within 24 hours; neuroimaging without tissue injury
Pulmonary Vein Stenosis*	Severe PV stenosis ( $\geq 70\%$ reduction in the diameter of the PV) will be considered a primary adverse event and major complication of AF ablation.
Phrenic Nerve Paralysis	Absent phrenic nerve function as assessed by a sniff test. A phrenic nerve paralysis is considered to be permanent when it is documented to be present 12 months or longer following ablation.
Major Vascular Access Complication / Bleeding	Major Vascular Access Complication: Defined as a hematoma, an AV fistula or a pseudoaneurysm which requires intervention such as surgical repair or transfusion, prolongs the hospital stay, or requires hospital admission. Major Bleeding: A major complication of AF ablation if it requires and/or treated with transfusion or results in a 20% or greater fall in HCT.
Pericarditis	Major: results in effusion which leads to hemodynamic compromise or requires pericardiocentesis, prolongs hospitalization by more than 48 h, requires hospitalization, or persists for more than 30 days following the ablation procedure.
Pulmonary Edema (Respiratory Insufficiency)	Respiratory insufficiency resulting in pulmonary complications necessitating intubation or other significant intervention (including diuretics administered specifically for treating pulmonary edema or ICU hospitalization requiring oxygen administration but not intubation). Pneumonia (infiltrate, fever and leukocytosis) and Acute Respiratory Distress Syndrome are excluded from this definition.

Primary Adverse Event	Description / Criteria
Stroke/ Cerebrovascular Accident (CVA)	
Diagnosis:
 
 
• Rapid onset of a focal or global neurological deficit with at least one of the following: change in level of consciousness, hemiplegia, hemiparesis, numbness or sensory loss affecting one side of the body, dysphasia or aphasia, hemianopia, amaurosis fugax, or other neurological signs or symptoms consistent with stroke.
 
• Duration of a focal or global neurological deficit <math>\geq 24</math> h; or <math>< 24</math> h, if therapeutic intervention(s) were performed (e.g., thrombolytic therapy or intracranial angioplasty); OR available neuroimaging documents a new hemorrhage or infarct; or the neurological deficit results in death.
 
• No other readily identifiable non-stroke cause for the clinical presentation (e.g., brain tumor, trauma, infection, hypoglycemia, peripheral lesion, pharmacological influences).†
 
• Confirmation of the diagnosis by at least one of the following: Neurology or neurosurgical specialist; Neuroimaging procedure (MRI or CT scan or cerebral angiography); Lumbar puncture (i.e., spinal fluid analysis diagnostic of intracranial hemorrhage).
 
 
Definition: Stroke: (diagnosis as above, preferably with positive neuroimaging study)
 
 
• Minor—Modified Rankin score <math>< 2</math> at 30 and 90 days††
 
• Major—Modified Rankin score <math>\geq 2</math> at 30 and 90 days
 

Hospitalization (initial or prolonged)	Device or procedure related serious adverse event that prolongs or requires in patient hospitalization for more than 48 hours. Excludes hospitalization (initial & prolonged) solely due to arrhythmia (AF/AFL/AT) recurrence or due to nonurgent cardioversion (pharmacological or electrical).

\* Occurrence greater than one week (7 days) post-procedure shall be deemed Primary AE.

\*\* Hemodynamic compromise or instability is defined as Systolic blood pressure  $< 80$  mmHg

† Non-focal global encephalopathy will not be reported as a stroke without unequivocal evidence based upon neuroimaging studies.

†† mRS assessments should be made by qualified individuals according to a certification process. If there is discordance between the 30 and 90 day mRS, a final determination of major versus minor stroke will be adjudicated by an independent physician/committee.

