### Endpoint:

#### Primary Endpoints:

- **Safety**

Incidence of early onset Primary Adverse Events (PAEs) (within 7 days of an ablation procedure which uses the HELIOSTAR™ catheter). PAEs include the following adverse events (AEs) and are defined in section 9.2.3 of the protocol:

- Device or procedure related death\*
- Atrio-Esophageal Fistula\*
- Myocardial Infarction
- Cardiac Tamponade/Perforation\*
- Thromboembolism
- Stroke/ Cerebrovascular Accident (CVA)
- Transient Ischemic Attack (TIA)
- Phrenic Nerve Paralysis (permanent)
- Pulmonary Vein Stenosis\*
- Pericarditis
- Pulmonary Edema
- Major Vascular Access Complication/Bleeding
- Hospitalization (initial or prolonged)\*\*

\* Events are considered and analyzed as primary AEs **even if they occur greater than one week (7 days) post-procedure.**

\*\* Excludes hospitalization solely due to arrhythmia recurrence or non-medically urgent cardioversion.

- **Effectiveness**

Freedom from documented asymptomatic and symptomatic Atrial Fibrillation, Atrial Tachycardia, or Atrial Flutter of unknown origin+ episodes based on electrocardiographic data (≥30 seconds on arrhythmia

monitoring device) through the effectiveness evaluation period (91-365 days post index procedure). Additionally, if a subject meets any one of the following criteria, then the subject will be considered an effectiveness failure:

- Failure to achieve acute procedural success. Acute procedural success is defined as confirmation of entrance block in clinically relevant PVs (all PVs except those that are silent and/or cannot be cannulated) after adenosine and/or isoproterenol challenge (with or without the use of a focal catheter).
- Greater than 2 repeat ablations for AF/AT/AFL (of unknown origin\*) in the blanking period ( $\leq 90$  days post index procedure) or a repeat ablation or surgical treatment for AF/AT/AFL (of unknown origin\*) during the effectiveness evaluation period.
- Direct current (DC) cardioversion for AF/AT/AFL (of unknown origin\*) during the effectiveness evaluation period.
- Continuous AF/AT/AFL (except CTI dependent) on a standard 12-lead ECG during the effectiveness evaluation period.
- A Class I and/or Class III AAD is prescribed/taken for atrial arrhythmia other than CTI dependent AFL at any time beyond the 3-month follow-up visit window (i.e., at any time beyond day 105 to 365 post index procedure).
- Oral Amiodarone is prescribed post index ablation procedure.

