### 8.5. Repeat Procedures

Repeat procedures may be performed at the discretion of the investigator. Repeat procedures during the blanking period (90 days post index procedure) must be conducted with the investigational device, with or without focal touch-up, if the arrhythmia is due to PV triggers. Repeat procedures performed after the blanking period may be managed per investigator discretion using a commercially available ablation catheter and generator. The follow-up schedule will remain based on the initial ablation procedure. All pre-discharge and 7-day post-ablation assessments as summarized in Table 8.8A are to be collected for repeat procedures.

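### The tamponade component of the primary safety endpoint is anchored to the index procedure in Table 9.2.3A but to any HELIOSTAR procedure elsewhere, and its time window differs between the two places

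*Protocol*

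**What the plan says.** **Protocol Summary, Primary Endpoints, Safety.** The endpoint is the incidence of primary adverse events "within 7 days of an ablation procedure which uses the HELIOSTAR™ catheter". The list includes "Cardiac Tamponade/Perforation" with a single asterisk. The note to that asterisk begins "Events are considered and analyzed as primary AEs" and extends this to events later than 7 days after the procedure. It names no upper limit. The Summary refers to section 9.2.3 for definitions.

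**Protocol section 9.2.3, opening sentence.** A primary adverse event is a listed event in the first 7 days after an ablation that used an investigational device, unless the table indicates otherwise.

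**Protocol Table 9.2.3A, tamponade row.** The event is "The development of a significant pericardial effusion during or within 30 days of undergoing the index AF ablation procedure". The only mark on the row is the double asterisk, whose note is a blood-pressure definition: "Hemodynamic compromise or instability is defined as Systolic blood pressure" below 80 mmHg. The single asterisk, with the note "Occurrence greater than one week (7 days) post-procedure shall be deemed Primary AE", stands on death, atrio-esophageal fistula and PV stenosis, and not on tamponade.

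**Protocol section 8.5.** "Repeat procedures during the blanking period (90 days post index procedure) must be conducted with the investigational device". This requirement is limited to arrhythmia that PV triggers cause; focal touch-up may be added.

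**The concern.** One component of a primary endpoint has two anchors (any HELIOSTAR procedure, or the index procedure only) and two windows (beyond 7 days with no stated end, or 30 days). The protocol foresees repeat procedures with the device: up to two in the blanking period do not make a subject an effectiveness failure. Section 8.5 also requires pre-discharge and 7-day assessments after each repeat. The safety data are therefore collected, but the row, followed literally, keeps a tamponade from a later repeat out of the component meant to count it.

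This is a single-arm trial judged against a safety performance goal (SAP section 1), and a Clinical Events Committee adjudicates the primary safety events (Protocol section 9.6). If the texts disagree, the status of a real event could depend on which one is used, and the choice might be made after the event is known. Leaving an event out can only lower the observed safety rate.

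**Working it through.** No sample size, performance goal or error rate in the available text depends on the tamponade window, so there is no stated figure to reproduce. The check is to classify the same events under each text.

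**Step 1. Classification.** Days are counted from the index procedure.

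| Event | Summary (single asterisk, any HELIOSTAR procedure) | 7-day default of 9.2.3 (any device procedure) | Table row (30 days from index) |
|---|---|---|---|
| Repeat day 10, tamponade day 12 | counts | counts | counts |
| Repeat day 10, tamponade day 18 | counts | no | counts |
| Repeat day 25, tamponade day 32 | counts | counts | no |
| Repeat day 31, tamponade same day | counts | counts | no |
| Repeat day 60, tamponade same day | counts | counts | no |
| Repeat day 90, tamponade same day | counts | counts | no |
| No repeat, tamponade day 40 | counts | no | no |

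The repeats on days 31, 60 and 90 show the anchor problem: an event on the day of a HELIOSTAR procedure does not meet the row. The day 25 repeat shows that the gap opens slightly before day 31. The last line shows the window problem, which does not need a repeat.

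**Step 2. Scale.** Inputs:
- N = 400, the maximum number of evaluable subjects (SAP section 1).
- r = share of subjects with a HELIOSTAR repeat on days 31-90. The documents do not give it; assumed 1%, 5% or 10%.
- t = tamponade per procedure. The available text gives no HELIOSTAR rate. Protocol section 1.5.1 reports 0.2% to 3% for the second-generation cryoballoon and up to 5% for the laser balloon, so 0.2%, 1%, 3% and 5% are used.

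Formulas: expected events left out = N × r × t. Probability of at least one = 1 − (1 − r × t)^N. Largest shift in the subject-level rate = 100 × r × t percentage points.

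| r | t | Expected events left out | P(at least one) | Largest shift (points) |
|---|---|---|---|---|
| 1% | 0.2% | 400 × 0.01 × 0.002 = 0.008 | 0.008 | 0.002 |
| 1% | 1% | 0.04 | 0.039 | 0.01 |
| 1% | 3% | 0.12 | 0.113 | 0.03 |
| 1% | 5% | 0.2 | 0.181 | 0.05 |
| 5% | 0.2% | 0.04 | 0.039 | 0.01 |
| 5% | 1% | 400 × 0.05 × 0.01 = 0.2 | 0.181 | 0.05 |
| 5% | 3% | 0.6 | 0.451 | 0.15 |
| 5% | 5% | 1.0 | 0.633 | 0.25 |
| 10% | 0.2% | 0.08 | 0.077 | 0.02 |
| 10% | 1% | 0.4 | 0.330 | 0.1 |
| 10% | 3% | 1.2 | 0.699 | 0.3 |
| 10% | 5% | 400 × 0.10 × 0.05 = 2.0 | 0.865 | 0.5 |

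Nine of the twelve combinations give fewer than one event. One event is 1/400 = 0.25 points. For given r and t these are upper figures, because they assume that none of the events enters the composite through another component. Late tamponade without a repeat is not sized, because the documents give no rate for it.

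**The case against.** **The windows can be largely reconciled.** The Summary sends the reader to section 9.2.3, which allows the table to set its own window, and the tamponade row sets 30 days. The Summary asterisk lifts the 7-day cap but does not say that the event counts at any time. Read together, tamponade counts past day 7 and up to day 30. This is a fair reading, and it means that the 7-day default is not a third competing window. Two things remain: the asterisk is on tamponade in the Summary and missing from the row, and the 30 days still run from the index procedure while both general statements run from any procedure with the device.

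**Other components catch some events.** A device- or procedure-related death, a major pericarditis with effusion, or a related hospitalization over 48 hours would still put the subject in the composite. This is right, so a reader should not infer that every such tamponade disappears from the safety rate. A drained tamponade, or a 1 cm effusion, without those features need not qualify elsewhere.

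**Other texts may settle it.** Protocol section 3.2.1, the statistical section, most of the SAP and the committee charter are not available here. They may contain a working rule, so how adjudicators would in fact classify an event cannot be known. That would not remove the contradiction between the Summary, section 9.2.3 and its table.

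**Minor effusions.** A reader might also infer that section 9.2.1 lets a large effusion escape reporting, because it exempts "A trace / trivial / minor pericardial effusion that is asymptomatic, requires no medical intervention, and does not extend hospitalization" without a size limit. The text does not support this as an error. The table calls an effusion of 1 cm or more significant, and an effusion so defined is not naturally read as minor. A numeric limit there would be a clarity preference.

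**Conclusion.** The inconsistency is in the current text and affects a primary endpoint component. On the literal wording of the row, a tamponade caused by a HELIOSTAR repeat on days 31-90 is left out of that component, although the Summary and the opening of section 9.2.3 cover it. A tamponade more than 30 days after the index procedure is classified differently by the Summary footnote and the row.

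The size is small. Over the assumed ranges, 0.008 to 2.0 events would be left out at N = 400, and well under one under most combinations. The repeat rate is an assumption, and the tamponade rates come from other balloons. One event moves the rate by 0.25 points at 400 subjects, and by more if the adaptive design stops at a smaller number. Any bias is downward, but small and only possible.

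A reader might note that days 31-90 are 60 of the 90 blanking days and infer that about two thirds of repeat-related tamponade is lost. That is a share of calendar days. The documents give no timing of repeats or of risk, and the device is mandatory only for repeats due to PV triggers. Nor do the documents support a claim that power or the sample size is affected. This is a wording error that should be corrected; it does not undermine the design.

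**What to change.** 1. **Anchor.** In the tamponade row of Table 9.2.3A, replace the reference to the index ablation with any ablation procedure in which the HELIOSTAR catheter was used, index or repeat. This agrees with the Summary and the opening of section 9.2.3.

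2. **Window.** State one window in both places, by one of two routes:
   - keep 30 days in the row, and state the 30-day limit for tamponade in the footnote to the Summary endpoint list; or
   - delete the 30-day limit from the row and add the single asterisk there.

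   Adding the asterisk while leaving 30 days in the row would keep the ambiguity. The double asterisk stays in either case, because it only defines hemodynamic compromise.

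3. **Consistency.** Check Protocol section 3.2.1, the SAP and the committee charter for the same wording, and align them if needed, before further tamponade events are adjudicated.

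The cost is a wording amendment. No new data are needed, because adverse events are recorded from consent to the last day of participation (Protocol section 9.4). The reported safety rate may become slightly less favourable.
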